## NON-INTERVENTIONAL (NI) STUDY PROTOCOL

### Study information

Title	Incidence of selected adverse events in a population-based Danish cohort with atopic dermatitis treated with conventional systemic therapies: a matched case-cohort study.
Protocol number	B3211007
Protocol version identifier	1.0
Date	04 November 2025
EU Post Authorization Study (PAS) register number	1000000628
Active substance	Methotrexate L01BA01 / L04AX03
Medicinal product	Methotrexate [REDACTED] [REDACTED]
Research question and objectives	
Research questions to be addressed by this study are as follows:
 
What is the incident rate of major adverse cardiovascular events (MACE) and malignancy (excluding non-melanoma skin cancer (NMSC)) per individual conventional systemic treatment in a dermatologist-verified adult atopic dermatitis (AD) patient population?
 
What are the incident rates of additional adverse events of special interest (All-cause mortality, Arterial thromboembolisms, Venous thromboembolisms, Dyslipidemia, Herpes zoster, NMSC, Serious infections) per individual conventional systemic treatment in a dermatologist-verified adult atopic dermatitis (AD) patient population?
 
What is the identified incident rates of above adverse events compared to the following two matched cohorts: The Danish background population AND Patients diagnosed with AD not receiving systemic therapies?

090177e1a4d83c92\Approved\Approved On: 11-Nov-2025 17:27 (GMT)

090177e1a4d83c92\Approved\Approved On: 11-Nov-2025 17:27 (GMT)

	
Primary Objective:          The primary objective is to quantify the incident rate of major adverse cardiovascular events (MACE) and malignancy (excluding non-melanoma skin cancer (NMSC)) per individual conventional systemic treatment in a dermatologist-verified adult atopic dermatitis (AD) patient population.
 
Secondary Objective:          The secondary objective is to quantify the incident rates of additional adverse events of special interest (All-cause mortality, Arterial thromboembolisms, Venous thromboembolisms, Dyslipidemia, Herpes zoster, NMSC, Serious infections,) per individual conventional systemic treatment in a dermatologist-verified adult atopic dermatitis (AD) patient population.
 
Tertiary Objective          The tertiary objective is to compare the above identified incident rates of adverse events per individual conventional systemic treatment in a dermatologist-verified adult atopic dermatitis (AD) patient population with the following two matched cohorts: The Danish background population AND Patients diagnosed with AD not receiving systemic therapies (see section 9.7).

Country(ies) of study	Denmark
Author	

 

 

This document contains confidential information belonging to Pfizer. Except as otherwise agreed to in writing, by accepting or reviewing this document, you agree to hold this information in confidence and not copy or disclose it to others (except where required by applicable law) or use it for unauthorized purposes. In the event of any actual or suspected breach of this obligation, Pfizer must be promptly notified.

## 1. LIST OF ABBREVIATIONS

Abbreviation	Definition
AD	Atopic Dermatitis
AT	Arterial Thromboembolisms
ATC	Anatomical Therapeutical Chemical
CABG	Coronary Artery Bypass Grafting
CPR	Civil Personal Register (unique Danish personal ID number)
CNS	Central Nervous System
CV	Cardiovascular
DVT	Deep Vein Thrombosis
DNPR	Danish National Patient Registry
DMARDs	Disease-Modifying Antirheumatic Drugs
EC	Ethics Committee
EMA	European Medicines Agency
ENCePP	European Network of Centres for Pharmacoepidemiology and Pharmacovigilance
HMA	Heads of Medicines Agencies
ICD	International Classification of Diseases
IQR	Interquartile Range
IR	Incidence Rate
IRB	Institutional Review Board
ITT	Intention-To-Treat

090177e1a4d83c92\Approved\Approved On: 11-Nov-2025 17:27 (GMT)

JAKi	Janus Kinase Inhibitors
MACE	Major Adverse Cardiovascular Events
NCSP	Nordic Medico-Statistical Committee Classification of Surgical Procedures
NMSC	Non-Melanoma Skin Cancer
PAS	Post Authorization Study
PCI	Percutaneous Coronary Intervention
PE	Pulmonary Embolism
PH	Proportional Hazards
PS	Propensity Score
PSO	Psoriasis
RA	Rheumatoid Arthritis
RWD	Real World Data
SAS	Statistical Analysis System
SD	Standard Deviation
SKS	Danish Classification of Health Care Procedures (Sundhedsvæsenets Klassifikations System)
SOP	Standard Operating Procedure
URTI	Upper Respiratory Tract Infection
UTI	Urinary Tract Infection
VTE	Venous Thromboembolism

090177e1a4d83c92\Approved\Approved On: 11-Nov-2025 17:27 (GMT)

### 3. ABSTRACT

**Title:** Incidence of selected adverse events in a population-based Danish cohort with atopic dermatitis treated with conventional systemic therapies: a matched case-cohort study.

Version 1.0, 04-NOV-2025, [REDACTED]  
[REDACTED]

**Rationale and Background:** Conventional systemic treatments are commonly used as first-line immunosuppressive therapy for AD in Denmark, despite being prescribed off-label and lacking AD-specific safety data. Existing safety data on conventional treatments are largely derived from other conditions such as rheumatoid arthritis or psoriasis. Therefore, generating safety data specific to AD is needed to close the data gap.

**Research question and objectives:**

What is the incident rate of major adverse cardiovascular events (MACE) and malignancy (excluding non-melanoma skin cancer (NMSC)) per individual conventional systemic treatment in a dermatologist-verified adult atopic dermatitis (AD) patient population?

What are the incident rates of additional adverse events of special interest (All-cause mortality, Arterial thromboembolisms, Venous thromboembolisms, Dyslipidemia, Herpes zoster, NMSC, Serious infections) per individual conventional systemic treatment in a dermatologist-verified adult atopic dermatitis (AD) patient population?

What is the identified incident rates of above adverse events compared to the following two matched cohorts: The Danish background population AND Patients diagnosed with AD not receiving systemic therapies?

**PRIMARY OBJECTIVE:**

The primary objective is to quantify the incident rate of major adverse cardiovascular events (MACE) and malignancy (excluding non-melanoma skin cancer (NMSC)) per individual conventional systemic treatment in a dermatologist-verified adult atopic dermatitis (AD) patient population.

**SECONDARY OBJECTIVE:**

The secondary objective is to quantify the incident rates of additional adverse events of special interest (All-cause mortality, Arterial thromboembolisms, Venous thromboembolisms, Dyslipidemia, Herpes zoster, NMSC, Serious infections,) per individual conventional systemic treatment in a dermatologist-verified adult atopic dermatitis (AD) patient population.

**TERTIARY OBJECTIVE**

The tertiary objective is to compare the above identified incident rates of adverse events per individual conventional systemic treatment in a dermatologist-verified adult atopic dermatitis

(AD) patient population with the following two matched cohorts: The Danish background population AND Patients diagnosed with AD not receiving systemic therapies (see section 9.7).

**Study Design:** This is a retrospective observational cohort register study.

**Population:** Patients with AD verified by a dermatologist and a background population

**Variables:** Variables include diagnosis for AD (and relevant diagnosis to be excluded), treatment for AD, i.e. conventional systemic therapies (exposures) and advanced therapies (exclusion criteria), outcomes, i.e. adverse events of special interest, including MACE, malignancies (excluding and including non-melanoma skin cancer), serious infections, venous thromboembolism (deep vein thrombosis and pulmonary embolism), dyslipidemia, and herpes zoster, and medical history (key covariates), i.e. alcohol abuse, cardiovascular disease (including heart failure and coronary heart disease), diabetes, dyslipidemia, prior cancer, hypertension, and smoking status.

**Data source:** The Danish National Registries including the Danish National Patient Registry, the Danish Register of Medicinal Product Statistics, the National Cause of Death Registry, and the National Population Registry.

**Study size:** All patients meeting the inclusion criteria will be included for the current data analysis. Since this is a descriptive, retrospective study, no sample-size calculation is performed.

**Data analysis:** Descriptive statistics will summarize patient characteristics using frequencies for categorical variables and means with standard deviations or medians with interquartile ranges for continuous variables.

Incidence rates of outcomes will be reported per 10,000 person-years with 95% confidence intervals.

The groups will be compared using a Cox-regression models. The proportionality assumptions will be tested using Schoefeld test and plots. If the PH assumption is violated, we will allow time-varying effects by including covariate $\times$ log(time) interactions or using time-split intervals. Use of competing-risk models will be employed where relevant and feasible. The statistical analysis will be captured in a statistical report with aggregated data in tables. In the primary analyses, overlapping events will be attributed to the drug to which the patient has been exposed for the longest duration.

P-values may be reported when relevant for descriptive purposes and will not be adjusted for multiple testing; they are presented as descriptive statistics only, and no hypotheses are being tested.

A sensitivity analysis will be conducted requiring only one use of a drug to fulfil the inclusion criteria.

To evaluate the robustness of the method applied to handle overlapping events in the primary analysis, multiple sensitivity analyses will be performed, in which overlapping events will alternatively be assigned to (a) the most recently administered drug, (b) attributed to both drugs, or (c) excluded by censoring the patient at the time of the event. These results will be presented separately.

Furthermore, a sensitivity analyses will be conducted reporting incidence rates for the years 1995-2001, 2002-2008, 2009-2015, and 2016-2022.

As a sensitivity analyses, a cox regression model with inverse Probability Treatment Weighting will be conducted.

**Milestones:**

Start of data collection: 07 November 2025

End of data collection: 30 November 2025

Registration in the HMA-EMA Catalogues of RWD studies: 06 November 2025

Final study report: 31 December 2025

090177e1a4d83c92\Approved\Approved On: 11-Nov-2025 17:27 (GMT)

#### **4. AMENDMENTS AND UPDATES**

None

090177e1a4d83c92\Approved\Approved On: 11-Nov-2025 17:27 (GMT)

## 5. MILESTONES

Milestone	Planned Date
Start of data collection	07 November 2025
End of data collection	30 November 2025
Registration in the HMA-EMA Catalogues of RWD studies	06 November 2025
Final study report.	31 December 2025

## 6. RATIONALE AND BACKGROUND

This noninterventional study is designated as a PASS and is conducted voluntarily by Pfizer. This study is not a commitment or requirement to any regulatory authority.

Conventional systemic treatments are the first step when initiating systemic immune suppression therapies for atopic dermatitis in Denmark. Although these therapies have been used for many years, they are prescribed off-label, resulting in a lack of published safety data in an AD population. In contrast, there is ample data on the safety of advanced therapies such as biologics and JAKis. Most published safety data on conventional systemic therapies instead come from other conditions including but not limited to RA or PSO. Hence, these therapies might exhibit a significantly different safety profile in AD patients compared to other patient populations. A literature search was conducted on September 16th, 2025 in Embase <1974 to 2025 September 12>, Ovid MEDLINE(R) ALL <1946 to September 15, 2025> for patients with M2S AD treated with conventional systemic treatments found a few reports of small case studies, while a search for studies including a similar amount of patients as in the proposed study (>5000 patients) did not detect any study. Obtaining safety data on the conventional systemic therapies is therefore essential for the treating healthcare professional to make an informed decision on choice of treatment. Obtaining safety data on the conventional systemic therapies is therefore essential for the treating healthcare professional to make an informed decision on choice of treatment.

The current protocol is designated as a PASS per CT34-POL Post-Authorization Safety Studies (PASS) for Methotrexat® "Lederle", that is approved for use for active rheumatoid arthritis in adult patients, for polyarthritic forms of severe, active juvenile idiopathic arthritis (JIA) when the response to non-steroidal anti-inflammatory drugs (NSAIDs) was inadequate, and for severe, refractory, disabling psoriasis that does not respond adequately to other forms of therapy such as phototherapy, PUVA therapy and retinoids, as well as severe psoriatic arthritis in adult patients, but not for AD. Regarding the safety profile of Lederle, the most common adverse events ( $\geq 1/100$ ,  $< 1/10$ ) are loss of appetite, nausea, vomiting, abdominal pain, inflammation and ulceration of the mucosa of mouth and throat, stomatitis, dyspepsia, and increase in liver-related enzymes (ALAT [GPT], ASAT [GOT], alkaline phosphatase and bilirubin).

090177e1a4d83c92\Approved\Approved On: 11-Nov-2025 17:27 (GMT)

## 7. RESEARCH QUESTION AND OBJECTIVES

Research questions to be addressed by this study are as follows:

What is the incident rate of major adverse cardiovascular events (MACE) and malignancy (excluding non-melanoma skin cancer (NMSC)) per individual conventional systemic treatment in a dermatologist-verified adult atopic dermatitis (AD) patient population?

What are the incident rates of additional adverse events of special interest (All-cause mortality, Arterial thromboembolisms, Venous thromboembolisms, Dyslipidemia, Herpes zoster, NMSC, Serious infections) per individual conventional systemic treatment in a dermatologist-verified adult atopic dermatitis (AD) patient population?

What is the identified incident rates of above adverse events compared to the following two matched cohorts: The Danish background population AND Patients diagnosed with AD not receiving systemic therapies?

### Primary Objective:

The primary objective is to quantify the incident rate of major adverse cardiovascular events (MACE) and malignancy (excluding non-melanoma skin cancer (NMSC)) per individual conventional systemic treatment in a dermatologist-verified adult atopic dermatitis (AD) patient population.

### Secondary Objective:

The secondary objective is to quantify the incident rates of additional adverse events of special interest (All-cause mortality, Arterial thromboembolisms, Venous thromboembolisms, Dyslipidemia, Herpes zoster, NMSC, Serious infections,) per individual conventional systemic treatment in a dermatologist-verified adult atopic dermatitis (AD) patient population.

### Tertiary Objective

The tertiary objective is to compare the above identified incident rates of adverse events per individual conventional systemic treatment in a dermatologist-verified adult atopic dermatitis (AD) patient population with the following two matched cohorts: The Danish background population AND Patients diagnosed with AD not receiving systemic therapies (see section 9.7).

## 8. RESEARCH METHODS

### 8.1. Study Design

This is a retrospective register study employing a matched cohort design. This study design was selected to reflect real world usage by utilizing the high-quality registries in Denmark with detailed information on patients with AD. This allows for retrospective analysis of a large number of patients and gives the possibility for comparing with cohort matched control groups (see details below and in section 9.2): the database includes information about close to 13.000 adult patients with a hospital diagnosis of AD. In addition, the database contains information about the general adult population estimated to 4.2 million in 2019. Hence a retrospective study design is more feasible than a prospective design. By matching adult AD patients on conventional systemic therapy with two comparator cohorts – the general Danish population and dermatologist-verified AD patients not receiving systemic treatment – the study contextualizes adverse event rates and isolates the treatment's effect. The general population cohort provides background incidence rates, and the untreated AD cohort helps distinguish the baseline risk from AD itself versus any additional risk due to systemic therapy. Matching on key factors (e.g., age, sex, and cardiovascular risk factors) further enhances methodological rigor by reducing confounding, making the safety outcome comparisons more reliable and clinically meaningful.

Patients with a diagnosis of AD (Table I) are included using the inclusion and exclusion criteria specified in 9.2. AD patients will be matched with individuals from the general population and patients with AD not treated with a systemic to enable relevant comparisons to further investigate safety data in the AD population.

#### Primary endpoints

- Reporting of incidence rates for a composite endpoint of major adverse cardiovascular events (MACE) and malignancy (excluding non-melanoma skin cancer (NMSC))

#### Secondary endpoints

Reporting of detailed event-by-event incidence rates

- All-cause mortality
- Arterial thromboembolisms
- Venous thromboembolisms
- Dyslipidemia
- Herpes zoster
- NMSC
- Serious infections
- MACE [primary]
- Malignancies (excl. NMSC) [primary]

### Tertiary Endpoints

- Comparison of the identified adverse events per individual conventional treatment (table II) with the following two matched groups:
  - a cohort-matched general Danish population
  - a cohort-matched patients with AD not receiving systemic treatment (Patients may only be included in one of the study groups).

## 8.2. Setting

### Persons and place:

The Danish health-care system is public and tax funded. It offers equal access to health services throughout the primary, secondary, and tertiary sector. At birth or upon immigration, all Danish residents receive a unique personal identification number. An anonymized identifier based on this number is used across national databases, allowing for accurate linkage of patient data. The linked data can then be accessed via Statistics Denmark where anonymized grouped data can be requested.

### Representativeness:

Statistic Denmark is comprised of data from the entire country. The database includes information about patients with a hospital diagnosis of AD. This number has recently been estimated to be close to 13.000 adult patients.

The aim of this study is to investigate a) the incident rate of major adverse cardiovascular events (MACE) and malignancy (excluding non-melanoma skin cancer (NMSC)) per individual conventional systemic treatment in a dermatologist-verified adult atopic dermatitis (AD) patient population, b) the incident rates of additional adverse events of special interest (All-cause mortality, Arterial thromboembolisms, Venous thromboembolisms, Dyslipidemia, Herpes zoster, NMSC, Serious infections) per individual conventional systemic treatment in a dermatologist-verified adult atopic dermatitis (AD) patient population and c) compare the identified incident rates of above adverse events to the following two matched cohorts: The Danish background population AND Patients diagnosed with AD not receiving systemic therapies.

Only patients with moderate to severe AD are in scope of the conventional systemic treatments. Hence the cohort of interest will be representative of the moderate to severe AD patients diagnosed in hospital setting by dermatologists and who are candidates to receive conventional systemic treatment. For the comparison groups consisting of AD patients not receiving conventional systemic therapy, this group will be representative of patients diagnosed in hospital setting by dermatologists and who have not received conventional systemic treatment. The comparison group consisting of the Danish background population will be representative of the Danish adult population without AD diagnosed in hospital setting by dermatologists.

This will be specific for AEs that occur more frequently than one in 13,000 patients. A cohort of approximately 13,000 adult patients with atopic dermatitis is expected to be sufficient for evaluating major adverse cardiovascular events (MACE) in this non-interventional safety study. Danish registry-based studies have demonstrated that cohorts of similar or smaller size can detect meaningful differences in MACE incidence, especially among patients receiving systemic therapies. With expected MACE rates around 1.5% annually in AD populations, this sample size should yield over 100 events per year, enabling robust risk estimation and subgroup comparisons. This aligns with epidemiological evidence and supports the adequacy of the proposed study population for assessing cardiovascular safety.

**Inclusion and exclusion criteria rationale:**

The aim of this study is to investigate specific adverse events following treatment with conventional systemic therapies (see section 8). The inclusion and exclusion criteria (see section 9.2.1 for details) have been designed to ensure the highest likelihood that any observed adverse events can be attributed to treatment with a conventional systemic therapy aimed at treating AD.

**Inclusion criteria rationale:**

The objective is to increase the probability that the included patients have an accurate diagnosis (criteria 2) and are actively filling their prescriptions (criteria 3); this strategy may create a more selective cohort but seeks to ensure superior data quality.

**Exclusion criteria rationale:**

The aim is to ensure that the adverse events registered cannot be attributed to any current or previous cases of cancer (criteria 1), other treatments (criteria 2 and 3), or other inflammatory diseases and their treatments (criteria 4). Additionally, it ensures that systemic treatments are administered specifically for AD and not for any other condition (criteria 4).

Given the high number of AD patients in the registry combined with previous experience each treatment group it is expected to comprise around 1000 patients for the majority of treatments.

**Time period**

The study period runs from January 1st, 1995, through December 31st, 2022. In the main analyses, patients are included if they have been diagnosed with AD by a dermatologist in a hospital setting and received the same conventional systemic therapy twice (Table II).

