**Cohort entry (index date) for exposed:**

- 1) Date of initiation of the second administration/filled prescription of the conventional systemic therapy for AD,
- 2) Last inclusion date is December 31st, 2021, to allow for a minimum of one year of follow-up.

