CVD Risk Factors					

090177e1a4d83c92ApprovedApproved On: 11-Nov-2025 17:27 (GMT)

History of coronary heart disease 	medical history	National Patient registry	NA	I20-I25	PCI (KFNG00, KFNG02, KFNG02A, KFNG05, KFNG05A, KFNG10, KFNG12, KFNG20, KFNG22, KFNG30, KFNG40, KFNG96, KZFX01) or CABG (KFNA, KFNB, KFNC, KFND, KFNE, KFNF, KFNH, KFNJ, KFNK, KFNW)
Diabetes	medical history	National Patient registry	250	E10-E14 (pre-defined macro)	NA
Dyslipidemia (within the past 5 years)	medical history	National Patient registry	NA	E78 (pre-defined macro)	NA
History of cancer	medical history	National Patient registry	140-209	C00-C96	NA
Hypertension	medical history	National Patient registry	400-404 (pre-defined macro)	I10.x-I15.x (pre-defined macro)	NA
Smoking history	medical history	National Patient registry	NA	Pre-defined macro	NA

Table V. ICD-10 Serious infection (see table III, role for all: AE and Secondary Outcome; Data Source: National Patient Registry)

Serious infections	Operational Definition: ICD-10
CNS infections	A02.21, A06.6, A17.0, A20.3, A27.81, A32.1, A39.0, A80-A89, B00.3, B00.4, B01.0, B01.1, B02.0-B02.2, B05.0, B05.1, B06.0, B26.1, B26.2, B10.01, B37.5, B38.4, B43.1, B45.1, B46.1, B58.29, G00-G08

090177e1a4d83c92\Approved\Approved On: 11-Nov-2025 17:27 (GMT)

Gastrointestinal infections	A00, A01, A02.0, A02.8, A02.9, A03-A05, A06.0, A06.2-A06.4, A07-A09, A21.3, A22.2, A42.1, B05.4, B15-B19, B25.1, B46.2, K35, K37, K57, K61, K62.0, K65.0, K65.9, K67, K75.0, K81.0, K81.8, K81.9
Gynecological infections	N70.0, N70.9, N71.0, N71.9, N72, N73.0, N73.2, N73.3, N75.5, N73.8, N73.9, N74
Heart infections	A32.8, B33.21, B37.6, I00, I01, I30, I32, I33, I38-I41, I43.0
Hepatitis	B16, B17, B18
HIV	B20-B24
Musculoskeletal infections	A02.23, H05.029, M00-M03, M46.2, M46.3, M46.5, M46.6, M60.0, M65.0, M65.1, M71.0, M71.1, M86.0-M86.2, M86.8, M86.9, M90.0, M90.1, M90.2
Opportunistic infections	A02, A07.2, A07.3, A15-A19, A27.0, A31, A32, A40.3, A42-A44, A48.1, A48.1, A60.0, A81.2, B00-B02, B17.9, B25, B27.1, B37-B40, B44, B45, B55, B58, B59, B78, B95.3, G02.0, G02.1, J13, J17.1, J17.2, K23.0, K67.3, K93.0
Pulmonary infections	A48.1, A37, B39-B40, B01.2, B05.2, B25.0, B44, B58.3, B59, B95.3, J10-J22, J85, J86, U04
Sepsis	A02.1, A20.7, A22.7, A24.1, A26.7, A28.2B, A32.7, A40, A41, A42.7, B37.7, R65.0, R65.1, R65.9

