### **Registries utilized in this study:**

The Danish National Patient Registry (DNPR) holds information on inpatient visits (since 1977) and outpatient visits (since 1995), along with data on medical procedures, including hospital-administered biologics and phototherapy. Diagnoses are recorded based on the International Classification of Diseases (ICD-8 from 1977 to 1993 and ICD-10 from 1994 onward). Hospital-administered procedures and treatments are registered using the SKS codes, while surgical procedures have been recorded according to the NOMECCO Classification of Surgical Procedures (NCSP) since 1996.

The Danish Register of Medicinal Product Statistics contains information on all filled prescriptions at community pharmacies from 1995 onwards, using the Anatomical Therapeutic Chemical (ATC) classification system.

The National Cause of Death Registry holds information on the cause and date of death when applicable.

The National Population Registry contains demographic information, including vital status and gender.

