## Events

During the treatment series, an adverse event can be adjudicated to the ongoing treatment. In the intention-to-treatment (ITT) study design, the event can be adjudicated to the treatment initiated at the index date.

If a patient is receiving overlapping treatments, any adverse event occurring during both therapies will be adjudicated to the therapy the patient has been on for the longest duration. Such events are referred to as overlapping events.

In the primary analyses, for overlapping events, the event is assigned to the drug the patient has been on the longest.

Multiple sensitivity analyses will be conducted to address overlapping events:

- The event is assigned to the most recent drug.
- The event is attributed to both drugs.
- The event is attributed to neither drug and the patient is censored.

Serious infections are defined as those requiring hospital admission for more than one day (Table V), and infections with HIV, hepatitis B or C, tuberculosis, or infections resulting in death.

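### Entry opens when prescription and outpatient data begin, with no washout, so some early entrants are ongoing users who look new, and part of their history is invisible

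*Protocol*

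**What the plan says.** **Entry.** Protocol section 8.2, Time period: "The study period runs from January 1", 1995. Under Cohort entry, the index date is "Date of initiation of the second administration/filled prescription of the conventional systemic therapy for AD", and "Last inclusion date is December 31", 2021. Sections 8.2.1 and 8.2.2 contain no drug-free period, new-user rule or minimum registry history.

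**Data.** Section 8.4 says that the prescription register "contains information on all filled prescriptions at community pharmacies from 1995 onwards". The patient registry "holds information on inpatient visits (since 1977) and outpatient visits (since 1995"), coded in "ICD-8 from 1977 to 1993 and ICD-10 from 1994 onward".

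**History.** Section 8.2.2 excludes any history of four inflammatory diseases. Table I in section 8.3 defines them by ICD-10 codes alone. Table IV lists "Dyslipidemia (within the past 5 years") with E78 only and no ICD-8 code. Heart failure and coronary heart disease also lack ICD-8 codes.

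**Use of drug history.** In section 8.7, Events, the intention-to-treat analysis credits events to the drug taken to have been started at the index date. In the primary analysis, an event during overlapping treatments "will be adjudicated to the therapy the patient has been on for the longest duration".

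**The concern.** A patient already taking a study drug at the end of 1994 shows a first visible fill early in 1995 and enters at the second. In the data this person looks the same as someone who started in 1995. The ongoing user has, however, already passed through earlier exposure without being removed by an event, death or a change of drug. Mixing the two groups can pull down early on-treatment rates. It also makes the start of treatment assumed by the intention-to-treat analysis untrue for the ongoing users.

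The second issue is history. The exclusion rationale in section 8.2 relies on the criteria to rule out other inflammatory diseases as the reason for treatment or the source of events. A diagnosis recorded only before 1994 cannot be seen with the codes listed. Incomplete cardiovascular history can also weaken the matching, because having at least one cardiovascular risk factor is a candidate propensity-score variable (section 8.7, Matching). The limitations in section 8.9 mention none of this.

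**Working it through.** The protocol gives no figure to reproduce, so the check is date arithmetic on its own dates. It gives no separate first inclusion date, so entry is taken to open with the study period.

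**1. Entry window.** 1 January 1995 to 31 December 2021 is 27 × 365 + 7 leap days = 9,862 days.

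**2. Look-back at an index date of 1 January 1995** (index date minus start of the source):

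| Source | Starts | Look-back |
|---|---|---|
| Filled prescriptions | 1995 | 0 days |
| Outpatient contacts | 1995 | 0 days |
| ICD-10 codes | 1994 | 1 year |
| Inpatient contacts, where an ICD-8 code is listed | 1977 | 18 years |

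**3. Five-year dyslipidemia window.** With E78 as the only code, it is first complete at 1994 + 5 = 1 January 1999. Days before that: 4 × 365 + 1 = 1,461, and 1,461 / 9,862 = 14.8%. If outpatient contacts must be covered for all five years, the date is 1 January 2000: 1,461 + 365 = 1,826 days, and 1,826 / 9,862 = 18.5%.

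**4. The 1995-2001 calendar band** (section 8.7). It has 7 × 365 + 2 = 2,557 days. Of these, 1,461 / 2,557 = 57% lack the five-year ICD-10 window, and 1,826 / 2,557 = 71% lack it with outpatient contacts. The band therefore mixes index dates with and without full history.

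**5. Telling ongoing from new users.** Section 8.7 joins fills of the same drug up to 150 days apart into one series. For the first 150 days of 1995 (150 / 9,862 = 1.5% of the window), a first visible fill may therefore belong to a series that began earlier. This is a share of calendar time. It could hold a larger share of patients, because all continuing users surface there.

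**6. Longest-duration rule.** Suppose drug A was in use before 1995 and drug B started later. Counting A only from 1995 shortens its duration but leaves it longer than B, so the event goes to the same drug. The order is hidden mainly when both drugs were already in use when the data begin.

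**7. Variables less affected.** The cancer exclusion (Table III) and four of the eight Table IV variables (alcohol abuse, diabetes, cancer, hypertension) carry ICD-8 codes that reach inpatient contacts back to 1977.

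**The case against.** The best defence has several parts.

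- **No new-user design is claimed.** This is correct: the only numeric look-back is the five years for dyslipidemia. A drug look-back is only implied, by treating the index date as the start of treatment and by attributing events on time on drug.
- **The primary and secondary objectives are rates, and the calendar bands already report rates by period.** This stands in large part. The bands 2002-2008, 2009-2015 and 2016-2022 are largely clear of the start-up problem. They do not give the matched hazard ratios of the tertiary objective. The protocol also does not say whether they sort by index date or by time at risk; in the second case early entrants still contribute to later bands.
- **Missed exclusion diseases are partly corrected.** Section 8.7 censors follow-up when such a condition develops, so a later code would end it. This helps only from the date of that code.
- **Index date is a candidate matching variable.** If it is used, early entrants tend to be compared with people whose history is equally short. That reduces the imbalance but does not restore the missing history.
- **Few patients may qualify early.** Inclusion needs a hospital ICD-10 code for atopic dermatitis. If that code must precede the index date (the order is not stated), early 1995 entries would be scarce.

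Three stronger readings are tempting. A reader might infer that early entrants as a group are prevalent users, but genuine initiators also enter in 1995. A reader might infer that the longest-duration rule generally names the wrong drug. Step 6 shows otherwise, and section 8.7 plans three alternative attributions. A reader might infer that exclusions and matching on history fail altogether, but the ICD-8 codes in Tables III and IV contradict that.

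**Conclusion.** The point holds in a limited form. Entry begins when the drug data begin, and no washout is required, so an unknown number of early entrants are continuing users analysed as starters. The four-disease exclusion cannot see diagnoses recorded only before 1994. The dyslipidemia window is incomplete for 14.8% of the entry window, or 18.5% if outpatient contacts count.

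These are shares of calendar time. Turning them into shares of patients would need entries per year and treatment durations, which the protocol does not give, so no patient share is claimed. The effect should be concentrated in the 1995-2001 band and in any hazard ratio pooled over all years. It does not invalidate the study. It should still be corrected, because study start, index rule, eligibility and code lists are all fixed in this protocol and the change is small.

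**What to change.** 1. Use 1995 as look-back only. Require the first qualifying fill or administration of a drug to fall on or after 1 January 1996, with no fill of that drug in the preceding 365 days. The index date stays at the second fill. The date must be set on the first fill: a first index date of 1 January 1996 would put first fills in 1995 and their washout in 1994, where no fills are recorded.
2. State how this washout relates to the 150-day gap in section 8.7, for example that the washout governs cohort entry and the gap governs series after entry.
3. Add ICD-8 codes for the four exclusion diseases to Table I. For years before 1994 they reach inpatient contacts only.
4. Add a sensitivity analysis of rates and matched hazard ratios for index dates from 1 January 1999, or from 2000 if outpatient contacts are required.

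The cost is a date, a washout sentence, some code rows and one added analysis. About one entry year of 27 is lost (365 / 9,862 = 3.7% of the window), including some genuine 1995 initiators. A patient whose earlier use ended more than a year before the first qualifying fill would still count as new, so the rule should be described as new use after a drug-free year. The statement in section 8.4 that cardiovascular diagnoses are sufficiently valid since 2010 is a separate coding question and is not settled by this change.
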